### 6.2.2 Analysis of secondary objectives

The effect of randomization arm on endline prevalence of infection with any species of STH prevalent at baseline (2.1) will be analyzed using generalized estimating equations with Poisson family, robust variance and exchangeable correlation matrix and adjusted for individual-, household-, and cluster-level factors in Table 5 as detailed above. The effect of randomization arm on the proportion of clusters interrupting transmission of each STH species present at baseline (2.2), will be calculated by comparing the proportion of clusters in each arm in which transmission of each STH is successfully interrupted using a Fisher's exact test as detailed above.

### 6.2.3 Secondary analyses

Cluster-level correlates of transmission interruption (as defined by reaching a cluster prevalence of the predominant STH  $\leq 2\%$  24 months after stopping MDA) will be assessed using a modified Poisson regression. Key correlates of breaking the transmission of STH will include baseline prevalence, age distribution, population migration levels, treatment coverage and adherence, rates of open defecation and population density.

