### 3. STUDY METHODS

#### 3.1 TRIAL DESIGN

DeWorm3 is a multi-site community cluster randomized trial conducted in focal geographic areas in Benin, India and Malawi. At each site, 40 clusters are randomized to receive either three years of twice-annual community-wide mass drug administration (MDA) with albendazole, targeting all age groups, or the current standard of care targeted MDA strategy at the site (Table 1).

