### 3.3. SAMPLE SIZE

At each site, study areas were selected to correspond to an approximate minimum population of 80,000 to 100,000 people. The study sites were divided into 40 total clusters, 20 in the intervention arm (twice-annual community-wide MDA) and 20 in the control arm (targeted MDA). Cluster sizes vary according to administrative and / or geographic barriers but had a minimum size of 1,650 residents on the baseline census. The minimum cluster size was selected to reduce the probability of repeatedly sampling the same individuals at all three time points to <10%, allowing for 10% refusal rate and the exclusion of the Longitudinal Monitoring Cohort from the sampled population. Randomization of clusters to community-wide vs. school-age targeted MDA was performed within each site as above (Section 3.2.2).

Cross-sectional prevalence surveys at baseline and 6 months post-MDA will be conducted on a random sample of 500 individuals per cluster. The primary outcome assessment of prevalence at 24 months post-MDA will sample 1,000 people per cluster in order to precisely assess prevalence on a cluster-by-cluster basis.

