## SECTION 4: STATISTICAL PRINCIPLES

### 4.1 CONFIDENCE INTERVALS AND P VALUES

Descriptive statistics will be presented as counts and percentages for binary, ordinal and categorical variables, and as means and standard deviations or medians and interquartile ranges for continuous variables, as appropriate based on distributions. Prevalences will use the finite population correction to account for the large proportion sampled from each cluster, and will be presented with logit Wald confidence intervals.

P-values of  $<0.05$  will indicate statistical significance for all analyses.

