## SECTION 6: ANALYSIS

### 6.1 OUTCOME DEFINITIONS

The outcomes will be a) individual-level STH infection, defined as an individual's test result for the predominant STH (Objective 1.1) or any STH (Objective 2.1), and b) cluster-level transmission interruption, defined as a prevalence of the predominant STH species (Objective 1.2) or each STH species prevalent at baseline (Objective 2.2) of  $\leq 2\%$  with 95% confidence using a one-sided binomial test, as measured by qPCR 24 months after the final round of MDA.

We will classify each individual's infection status as negative (no amplification, Cycle threshold  $>40$ ), positive, or indeterminate; primary analyses will consider indeterminate results negative, while sensitivity analyses will recategorize indeterminate results as positive. Cycle thresholds indicating a positive or indeterminate result for each species will be defined and standardized by the DeWorm3 STH Molecular Support Unit.

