### 6.2 ANALYSIS METHODS

All analyses will be conducted separately for each site, unless otherwise specified.

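### SAP 6.2.3 models a yes/no interruption outcome on 40 clusters per site for six or more correlates, with no small-sample variance: false-positive rates run to about 1.7–4 times nominal if the ordinary sandwich is used, and power is low

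*SAP*

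**What the plan says.** SAP 6.2.3 takes as its outcome whether a cluster reaches a prevalence of the predominant species of 2% or less at 24 months. Correlates of that outcome "will be assessed using a modified Poisson regression". Those named are "baseline prevalence, age distribution, population migration levels, treatment coverage and adherence, rates of open defecation and population density": six, or seven if coverage and adherence are entered separately, and the wording leaves the list open. Randomization arm is not on it.

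SAP 6.2 sets the unit of analysis: "All analyses will be conducted separately for each site, unless otherwise specified". Section 6.2.3 specifies nothing else, and the pooled analysis in 6.2.1 concerns only the arm effect. SAP 3.1 gives the size of each fit: "At each site, 40 clusters are randomized", split 20 and 20 by SAP 3.3. Under SAP 4.1, P-values below 0.05 "will indicate statistical significance for all analyses".

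The outcome has two wordings. Section 6.2.3 says only that the cluster reaches 2% or less. SAP 6.1 requires this to be shown "with 95% confidence using a one-sided binomial test, as measured by qPCR 24 months after the final round of MDA".

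For this analysis the SAP does not state whether correlates enter jointly or one at a time, which variance estimator is used, whether arm is included, how multiplicity is handled, or how many interrupted clusters are expected. It does not label the analysis exploratory.

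**The concern.** Modified Poisson regression relies on a sandwich variance, which is justified in large samples. Here the sample is 40 clusters, and the information is limited further by the number of interrupted clusters. With six or seven coefficients and perhaps 4–19 events, the uncorrected sandwich tends to understate the standard errors. Null correlates then pass P<0.05 too often.

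The outcome also reduces 1,000 test results per cluster to a single yes or no, so a real correlate is hard to find. A list of key correlates of interruption is likely to be read as a guide to where community-wide treatment would work. A list that mixes chance findings with missed real ones would be a poor guide.

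**Working it through.** **The plan's own figure.** The documents give no power or error figure for 6.2.3, so I first checked the planning inputs on Objective 1.1 (SAP 3.3.1). The formula is c = 1 + (z_α/2 + z_β)² [π0(1−π0) + π1(1−π1)][1 + (m−1)ρ] / [m(π0−π1)²], with π1 = 2%, c = 15–20, m = 500 or 1,000 and ρ = 0.003–0.005. Solving for π0 gives 2.89% to 3.44%, which agrees with the stated 3% to 3.5%. At the low end (c = 20, m = 1,000, ρ = 0.003, π0 = 0.0289): 1 + 7.849 × 0.04767 × 3.997 / (1,000 × 0.0089²) = 19.9.

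**Events per site.** Inputs: 20 clusters per arm, 1,000 tested per cluster, ICC 0.003–0.005 and control prevalence 7% (SAP 3.3 and 3.3.1). Intervention prevalence of 1–2% is my assumption; SAP 3.3.1 lets it vary for Objective 1.2.

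Under the one-sided test of SAP 6.1, a cluster passes with at most 12 positives, since P(X≤12 | 1,000, 2%) = 0.038 and P(X≤13) = 0.064. Under the wording of 6.2.3 it passes with at most 20. Expected events are 20 × P(X ≤ limit), with X beta-binomial:

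| Intervention prevalence | At most 12 (SAP 6.1) | At most 20 (SAP 6.2.3) |
|---|---|---|
| 1.0% | 14 | 18–19 |
| 1.5% | 8.5–9.3 | 15–16 |
| 2.0% | 4.1–5.4 | about 12 |

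Control clusters at 7% add practically none. For comparison, the benchmark in Protocol 8.1 of half the intervention clusters gives 0.5 × 20 = 10.

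**False positives.** I simulated 40 clusters with six independent null correlates entered together, no arm term, a log-link Poisson model and Wald z tests at 0.05 (ICC 0.004, 2,000 runs per row). The last column is linear regression of log((positives + 0.5)/(tested + 1)) on the same correlates plus arm, with t tests.

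| Rule, intervention prevalence | Mean events | Ordinary sandwich (HC0), per correlate | HC0, at least one | HC3, per correlate | Linear on log prevalence, per correlate |
|---|---|---|---|---|---|
| ≤12, 1.0% | 14.1 | 10.0% | 44% | 3.3% | 5.6% |
| ≤12, 1.5% | 8.9 | 12.1% | 48% | 3.3% | 4.9% |
| ≤12, 2.0% | 4.8 | 17.2% | 58% | 1.6% | 5.2% |
| ≤20, 1.0% | 18.3 | 9.0% | 41% | 3.6% | 4.7% |
| ≤20, 1.5% | 15.5 | 8.9% | 39% | 3.2% | 4.9% |
| ≤20, 2.0% | 11.6 | 9.9% | 43% | 3.1% | 5.0% |

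In the third row 15% of runs gave no usable fit.

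With events fixed instead, six joint correlates give 15.9% at 5 events, 11.3% at 8 and 9.6% at 12; seven give 18.1% at 5 and 10.7% at 12. Across ICC 0.003–0.005 the range is 8.5–22%, so 8.5/5 = 1.7 to 22/5 = 4.4 times nominal, the top end only at 4–5 events. The chance of at least one false correlate reaches 66% with seven at 5 events. If each test held 5% it would be 1 − 0.95⁶ = 26% or 1 − 0.95⁷ = 30%.

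**Power.** I assumed one real correlate that shifts cluster prevalence by 0.2 log units per SD; the documents give no such figure. The yes/no model by site detects it in 9–42% of fits with HC0 and 3–13% with HC3. Linear regression of log prevalence detects it in 55–96% by site and 98–100% pooled over 3 × 40 = 120 clusters, with false positives at about 5%.

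**The case against.** Much of the opposing case stands.

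- **The inflation is conditional.** The event count, the joint model and the uncorrected variance are assumptions; the SAP fixes none of them. One-at-a-time models give 8.6–11.8% at 5–12 events with normally distributed correlates (about 13% with a skewed one). HC3 brings the rate below 5%. A reader might infer that modified Poisson regression is itself invalid here; the results show only that its uncorrected variance is.
- **The largest multiple needs the least favourable setting.** Rates of 16–22% need 4–5 events, which means intervention prevalence at the 2% threshold together with the SAP 6.1 test rule. Under the wording of 6.2.3, at 1–2%, inflation is about 1.7–2 times. With so few events, some fits would also fail visibly.
- **A spurious correlate in every site is not the expected result.** A reader might infer it. At 40–65% per site, and treating sites as independent, all three would show one with probability 0.40³ = 6% to 0.65³ = 27%. Part of the per-site figure is plain multiplicity.
- **The questions differ.** Log prevalence describes what moves prevalence anywhere, including well above 2%. Pooling joins sites whose predominant species may differ and whose standard of care does differ (SAP Table 1). This is a good reason not to drop the yes/no model or to rely on pooling alone.
- **The power comparison rests on an assumed effect** acting equally across arms and sites, which favours the linear model.

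What the objection does not answer is that HC3 cures the error rate only by leaving 3–13% power. The yes/no model by site is either too liberal or nearly uninformative.

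**Conclusion.** The concern holds in conditional form. With the correlates entered together and the ordinary sandwich variance, and assuming 1–2% intervention and 7% control prevalence, a null correlate is significant about 9–12% of the time at 8–19 events and 16–22% at 4–5 events. At least one false correlate per site has a chance of about 40–65%, against 26–30% at correct size. A small-sample variance repairs the error rate but not the loss of information.

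These figures assume 1,000 tested per cluster and independent correlates (a run with correlation 0.3 gave similar rates). They use unweighted counts, whereas the SAP endpoint is age- and gender-weighted.

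A reader might carry this over to the trial's main results; the documents do not support that. Objectives 1.1, 1.2, 2.1 and 2.2 are tested by other methods in SAP 6.2.1 and 6.2.2, and this analysis is tied to no numbered objective. It is worth changing because the list of correlates is likely to be used and the better analysis needs no new data.

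**What to change.** Amend SAP 6.2.3 in two parts.

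1. Keep the yes/no modified Poisson model, with a named small-sample variance such as HC3. State whether correlates enter jointly, which of the two outcome wordings applies, and that the results are exploratory or descriptive.
2. Add as the main correlates analysis a linear regression of log endline cluster prevalence on the listed correlates with an arm term. Prevalence should be age- and gender-weighted as in the SAP endpoint, with a small offset for zero counts. Fit it by site, and also pooled over the 120 clusters with site terms and checks of site-by-correlate interaction.

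The cost is SAP wording and modest analysis time on the same data. The downsides are that the added model describes correlates of endline prevalence rather than of crossing 2%, and that the pooled fit assumes similar associations across sites, which the interaction checks can only partly test. The linear model also does not remove multiplicity: six tests at 5% still give a 26% chance of at least one false finding, so estimates and intervals should be reported for every correlate, not only those below 0.05.

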## Statistical software

Analyses will be conducted in R and SAS.

